## 1. Rationale

After having demonstrated a sedative effect (1), a multi-center, double-blind, randomized, sham-controlled trial has shown the efficacy and safety of external trigeminal nerve stimulation (e-TNS) with the Cefaly® device as preventive treatment of episodic migraine (2). Safety and patient satisfaction have been confirmed by a prospective study on 2,313 patients (3). The Cefaly® device was FDA-approved for migraine prevention in 2014.

Post-marketing data and survey (7) showed that many patients in Europe use the Cefaly® device not only for migraine prevention but as well during migraine attack to reduce the headache pain intensity. Several studies have been recently performed on the Cefaly® device as an acute treatment of migraine with specific electrical neurostimulation parameters.

- A pilot trial on migraine patients was performed at the University of Liège (Liege, Belgium) (4). Patients were asked to apply the Cefaly® device for a 20-minute session as an acute treatment for 3 migraine attacks. e-TNS completely relieved the patients in 13% of attacks, allowed to postpone the intake of anti-migraine drugs by more than 30 minutes in 20%. Results were inconclusive. But the protocol was not designed appropriately regarding the efficient use of the device and the duration of the stimulation. In particular, using the device without training may have resulted in stimulation under the minimum threshold of efficacy. In addition, the stimulation session duration was only 20 minutes, which we know from migraineurs is not long enough to get pain relief during migraine attacks.
- Kozminsky (5) assessed whether the Cefaly® device was effective and well tolerated as rescue therapy for migraine symptoms lasting 72 hours or longer, and concluded that e-TNS therapy with the Cefaly® device brought about a reduction of migraine-related pain (average minus 46%) as rescue therapy in these patients. e-TNS therapy via the Cefaly® device was well tolerated, and most patients would consider home therapy if it was affordable.
- [name], at Columbia University, implemented an open-label pilot trial on the acute treatment of migraine with the Cefaly® e-TNS device (6). Thirty (30) patients having a migraine attack with or without aura were included in the modified intention-to-treat (mITT) analysis. In terms of safety, no adverse events or side effects were reported. In terms of efficacy, mean pain intensity was significantly reduced by 57.10% after the 1-hour e-TNS treatment (-3.22 ± 2.40; p<0.001) and by 52.84% at 2-hour time point (-2.98 ± 2.31; p<0.001). No patients took rescue medications within the 2-hour observation phase. Within the 24-hour follow-up, 34.62% of patients used a rescue medication. The findings from this open-label study suggest that e-TNS with the Cefaly® device is a safe and effective acute treatment for migraine, and merits further study with a double-blind, randomized, sham-controlled trial.

- University of Liege in Belgium (Prof. [name]) did a post-marketing survey on more than 800 regular users of the Cefaly® device in France, Switzerland and Belgium (7). 89.2% of responders to the questionnaire had been diagnosed by a physician as suffering from migraine. 88.6% of these patients reported to use the Cefaly® device during migraine attacks and that in 42.6% of these attacks, the use of the Cefaly® device prevented the intake of acute anti-migraine medication.
- [name] conducted a multicenter, double-blind, randomized, sham controlled trial on the acute treatment of migraine with the Cefaly® device. One hundred and six (106) patients having a migraine attack with or without aura were randomized and included in the intention-to-treat (ITT) analysis. Among them, ninety-nine (99) were eligible for the modified intention-to-treat (mITT) analysis i.e. randomized patients having had the 1-hour stimulation treatment and having given their headache pain intensity measurement at baseline and at 1-hour time points. The last value carried-forward method was used when needed. In terms of safety, one adverse event (nausea) occurred but this event was minor and totally reversible (nausea resolved by itself after 20 minutes). There was no serious adverse events (SAE), nor were any subjective complaints or side effects reported in either group within the 24 hours after the beginning of the treatment. In terms of efficacy, in the ITT analysis, the primary outcome, mean migraine pain intensity after the 1-hour e-TNS session compared to baseline, was very significantly more reduced in the verum group than in the sham group (-3.46±2.32 versus -1.78±1.89, p<0.001; or -59% versus -30%, p<0.001). This pain relief percentage was as well significantly reduced in the verum group compared to the sham group at 2 hours and 24 hours. In the mITT analysis, mean migraine pain intensity was as well very significantly more reduced in the verum group than in the sham group at 1hour (-3.83±2.13 versus -1.85±1.89, p<0.001; or -65% versus -32%, p<0.001) and at 2-hour and 24-hour time points. In addition, the percentage of pain free patients at 24-hour time point was significantly higher in the verum group compared with the sham group (32% versus 13%, p<0.05), and 30% sustained pain relief for 24 hours was significantly higher in the verum group compared to the sham group (43% versus 21%, p<0.05). Anti-migraine rescue medication intake within the 24 hours after the beginning of the treatment was not significantly lower in the verum group.

All these clinical data provide safety and efficacy evidence for e-TNS with the Cefaly® device in the acute treatment of migraine. Nevertheless, the evidences of efficacy were mainly reported for migraine patients treated in the clinic and for migraine lasting already for several hours. No data is available for patients using the device by themselves, at home, on a migraine attack at an early stage of its development. Such clinical data is therefore needed to assess the efficacy of the Cefaly® de vice as an acute migraine treatment at home, especially since migraine experts recommend patients to apply acute treatment of migraine at the beginning of the attack. An open pilot trial will allow to assess feasibility of the study design and provide data to prepare a phase 3 multicenter, randomized, controlled trial on the acute treatment of migraine at home by e-TNS with the Cefaly® device.

# 2. Study objective

The main objective of this study is to have a pilot assessment of the efficacy of the Cefaly® Abortive Program device used at home for 2 hours to treat a migraine attack, as triptans are generally used. That is to say having pilot data to assess the efficacy of the Cefaly® Abortive Program device in the abortive treatment of acute migraine as measured by 2-hour pain freedom, pain relief and migraine associated symptoms freedom, plus evolution of these measurements for 24 hours after the beginning of the treatment session.

# 3. Study outcomes

# 3.1. Efficacy outcomes

#### **Primary outcomes:**

- 1. Pain Freedom (PF) at 2 hours, defined as the percentage of patients having a reduction of a moderate or severe migraine headache (Grade 2 or 3) at baseline to no headache (Grade 0) at 2 hours after the beginning of the e-TNS session.
- 2. Most bothersome migraine-associated symptom (MBS) freedom at 2 hours, defined as the percentage of patients with absence, at 2 hours after the beginning of the e-TNS session, of the most bothersome migraine-associated symptom identified at baseline.

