#### 4.2.2. Acute treatment phase

During the 2 months following the screening visit, the patient will be instructed to treat a single qualifying migraine headache. A migraine headache is a qualifying migraine if all the following conditions are met:

- 1. The migraine headache severity is moderate or severe (Grade 2 or 3).
- 2. The migraine headache is associated with at least one of these migraine-associated symptoms: photophobia, phonophobia, nausea, vomiting.
- 3. The migraine headache started less than four hours ago or the patient woke up with migraine.
- 4. No other migraine headache or headache has occurred in the previous 48 hours.
- 5. The migraine headache is not already resolving on its own i.e. the pain is not already diminishing.
- 6. No acute anti-migraine medication has been taken since the beginning of the migraine headache.

In case of qualifying migraine, patient will have to apply the Cefaly® Abortive Program device for a complete treatment session of 2 hours as soon as the migraine headache is moderate or severe (Grade 2 or 3).

In his/her diary, the patient will note the headache pain severity on the following scale: 0 = no pain; 1 = mild pain; 2 = moderate pain; 3 = severe pain. The patient will note as well the migraine associated symptoms (photophobia, phonophobia, nausea, vomiting) and will specify which associated symptom is the most bothersome symptom (MBS). The patient will note this data just before the start of the Cefaly® Abortive Program (baseline data) and 2 hours after the beginning of the treatment session (normally just after removing the device and the electrode if the session ran correctly) (2-hour data), whatever the duration of the stimulation session. The patient will also have to record if any aura was associated with the qualifying migraine attack.

Devices will be programed for only 1 treatment session to be performed at home to treat the qualifying migraine.

The Cefaly® device will be programed with the following parameters (Abortive Program): square pulse current (100 Hz,  $250 \mu s$ ) at a linearly increasing intensity starting at 0 mA up to a maximum of 16 mA after 14 minutes, then remaining stable for the rest of the session (106 minutes).

Patients will be instructed to not take any acute anti-migraine medication during the acute treatment .

phase.

During the acute treatment phase, when the Cefaly® Abortive Program device stopped, it may not be

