#### 6.5. Medication during the trial

Patients will be instructed to not take any acute anti-migraine medication during the acute treatment phase. After the 2 hours acute treatment phase, if the patient has moderate or severe migraine

headache pain (Grade 2 or 3), he/she is allowed to take his/her own anti-migraine rescue medication. Use of acute medication will be recorded by the patient on the diary for the 24 hours following the beginning of the treatment.

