# 7. Practical study modalities

# 7.1. Efficacy outcome measures

The treatment efficacy outcomes will be assessed based on the following clinical data.

- **Headache pain severity.** In order to evaluate the modification of pain severity from baseline to 2-hour and 24-hour time points, patients will be asked to note their headache pain intensity on the following scale: 0 = no pain; 1 = mild pain; 2 = moderate pain; 3 = severe pain.
- **Migraine associated symptoms**. The patient will also note the presence of migraine associated symptoms (photophobia, phonophobia, nausea, vomiting) and will specify which associated symptom is the most bothersome symptom (MBS).
- **Rescue medication intake**. The patient will also record whether he/she took ANY acute rescue medication during the 24 hours following the beginning of the e-TNS session.

The following table depicts when the different measures will be made:

	At baseline, i.e. just before the beginning of the e-TNS session	2 hours after the beginning of the e-TNS session	24 hours after the beginning of the e-TNS session
Headache pain severity	•	•	•
Migraine associated symptoms	•	•	•
Most bothersome migraine associated symptom (MBS)	•		
Rescue medication intake			•

All clinical data will be collected on a paper diary and AE collecting form.

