8.2.1. Sample size

The sample size was computed based on the primary outcome, i.e. pain freedom at 2 hours. Results

from previous sham-controlled trial using the Cefaly® device as acute treatment of migraine reported

7,7% of pain freedom at 2 hours in the placebo group. In the current study, the pain freedom at 2 hours

associated with the Cefaly® Abortive Program treatment is expected to be similar to the results related to triptans, in particular to Lasmiditan that presented 32,2% of pain freedom at 2 hours.

A power analysis showed that a sample of 42 patients allows detecting a statistically significant difference between the expected (32,2%) and placebo (7,7%) pain freedom at 2 hours with a power of at least 80% and a 5% level of significance.

Taken into account a rate of 30% of patient loss during the study (based on the Lasmiditan study), at least 60 patients should be included in the study.

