#### 8.2.3. Statistical analysis

Modified intention-to-treat (mITT) analysis

Patient data will be included in the mITT analysis if all the four following conditions are met:

- 1. The patient treated a qualifying migraine.
- 2. The patient applied the Cefaly® Abortive Program treatment during at least one minute\*.
- 3. The headache pain severity score **AND** the migraine associated symptom(s) at baseline were reported in the diary.
- 4. The headache pain severity score **OR** the migraine associated symptom(s) at 2 hours were reported in the diary.

Data provided by Colucid Pharmaceuticals, Inc. and available on the following website: https://globenewswire.com/news-release/2016/09/06/869611/0/en/CoLucid-Pharmaceuticals-Announces-Achievement-of-Both-Primary-and-Key-Secondary-Endpoints-in-the-SAMURAI-Phase-3-Pivotal-Trial-of-Lasmiditan-in-Migraine.html (consulted in May 2017).

\*If the patient stopped the 2-hour treatment session before its end for any reason, he/she is kept in the modified intention-to-treat (mITT) analysis if all the other conditions are met.

If the patient takes rescue medication between 2 hours and 24 hours after the beginning of the e-TNS session, the headache pain intensity and associated symptoms presence can be affected by the medication and the last value carried forward method (2-hour value carried forward method in this case) will be applied for the 24-hour time point headache pain severity and migraine associated symptoms.

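### Acute medication taken between session start and the 2-hour rating is prohibited but has no scoring rule, so read literally such a patient can count as a device success; the likely effect is small

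*Combined protocol and SAP*

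**What the plan says.** **Outcomes (Section 3.1).** Pain freedom is the share of participants "having a reduction of a moderate or severe migraine headache (Grade 2 or 3) at baseline to no headache (Grade 0) at 2 hours", timed from session start. MBS freedom is the share who, at 2 hours, no longer have the symptom named as most bothersome at baseline. Secondary outcomes 1 and 2 (pain relief and symptom absence) are also read at 2 hours. None of these four carries a medication condition. Sustained pain freedom (secondary outcome 4) does: any rescue use in the 24 hours from session start fails it. Secondary outcome 3 counts rescue use only from 2 to 24 hours.

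**Intake before the session.** Condition 6 for a qualifying attack in Section 4.2.2 reads "No acute anti-migraine medication has been taken since the beginning of the migraine headache", and the first mITT condition in Section 8.2.3 is "The patient treated a qualifying migraine".

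**Intake during the session.** Sections 4.2.2 and 6.5 tell patients not to take acute medication in this phase. The 2-hour rating is made however long the session ran. Section 8.2.3 keeps anyone treated for at least one minute who meets the other conditions, whatever the reason for stopping.

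**Intake after 2 hours.** The only analysis rule for medication, in Section 8.2.3, begins "If the patient takes rescue medication between 2 hours and 24 hours after the beginning of the e-TNS session". It carries the 2-hour values forward to 24 hours, on the ground that "the headache pain intensity and associated symptoms presence can be affected by the medication".

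**Recording.** Section 7.1: "The patient will also record whether he/she took ANY acute rescue medication during the 24 hours following the beginning of the e-TNS session". Section 6.5: "Use of acute medication will be recorded by the patient on the diary for the 24 hours following the beginning of the treatment".

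**The concern.** Intake before the session is handled: it makes the attack non-qualifying and so removes the patient from the mITT set. Intake after 2 hours is handled for the 24-hour values. Intake in between has a prohibition but no consequence in the analysis, and that is the window in which a drug can change both primary outcomes.

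The plan accepts that medication can alter the ratings, yet applies this only to the 24-hour time point. The same patient can therefore succeed on the primary outcome and fail sustained pain freedom because of the same tablet.

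The trial is open-label, single-arm and conducted at home, so no control arm offsets a drug effect. The last paragraph of Section 1 says the data are meant to prepare a phase 3 trial. An upward error in the 2-hour rates would pass into that planning, and without a rule the scoring could be chosen after the results are known.

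**Working it through.** **Following one patient through the text.** Take a patient who starts the session on a qualifying attack, takes an acute drug part-way through, and records no pain and no MBS at 2 hours.

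1. Condition 6 was met when treatment started, so the attack qualified and mITT condition 1 is satisfied.
2. At least one minute of treatment was given, and the baseline and 2-hour ratings are in the diary, so mITT conditions 2 to 4 are satisfied.
3. The 2-hour rating is not missing, so the carry-forward rule in Section 8.2.2 does not apply. The medication rule in Section 8.2.3 starts at 2 hours, so it is not triggered.
4. Result: success on both primary outcomes, failure on sustained pain freedom, and not counted in secondary outcome 3.

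**The plan's own figures (Section 8.2.1).** A pooled two-proportion formula (7.7% against 32.2%, two-sided 5%, 80% power) gives 41 per group, within one of the stated 42. The enrolment figure is 42 / (1 − 0.30) = 60. The 42 serves here only as a divisor.

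**Inputs for the size.**
- Divisor: n = 42 (Section 8.2.1).
- Drug response: 32.2%, from the comparator rate, "in particular to Lasmiditan that presented 32,2% of pain freedom at 2 hours".
- Early intake r: not given for this trial. Section 1 says nobody in the earlier open-label pilot took rescue medication within 2 hours. Assumed range: 0 to the exact 95% upper limit for 0 of 30, which is 1 − 0.025^(1/30) = 11.57%. This is a limit, not an observed rate. The denominator for that item is not stated; 30 is the pilot's mITT size.
- Device-alone response d among early medicators: not given. Two cases: d = 0.322 (same as everyone else) and d = 0 (all are device failures).

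**Formulas.** Only a patient who would have failed on the device alone can inflate the rate.
- One such patient converted by the drug: 1/42 = 2.4 points.
- Inflation from as-observed scoring: r × (1 − d) × 0.322.
- Understatement from non-responder scoring: r × d.

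| Intake r | As-observed, d = 0.322 | Non-responder, d = 0.322 | As-observed, d = 0 | Non-responder, d = 0 |
|---|---|---|---|---|
| 0% | 0 | 0 | 0 | 0 |
| 5% | 0.05 × 0.678 × 0.322 = +1.1 | 0.05 × 0.322 = −1.6 | 0.05 × 0.322 = +1.6 | 0 |
| 11.57% | 0.1157 × 0.678 × 0.322 = +2.5 | 0.1157 × 0.322 = −3.7 | 0.1157 × 0.322 = +3.7 | 0 |

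Entries are percentage points of pain freedom.

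**Sensitivity.** Halving the drug response to 16.1%, because the drug has acted for less than 2 hours, halves the as-observed figures: 0.5 and 1.3 points for d = 0.322, and 0.8 and 1.9 for d = 0. If the pilot denominator was 26 (34.62% = 9/26), the limit is 13.23% and the largest as-observed figures become 0.1323 × 0.678 × 0.322 = 2.9 and 0.1323 × 0.322 = 4.3.

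**Comparison.** The planned contrast is 32.2 − 7.7 = 24.5 points. MBS freedom cannot be sized, because the documents give no expected MBS rate.

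**The case against.** **The plan can be read as excluding these patients.** Condition 6 refers to the time since the headache began, and mITT condition 1 requires a qualifying attack, so a statistician might drop in-session medicators. This reading is possible but less natural, since the condition decides whether an attack may be treated. It would also remove the patient rather than score them, which gives a different rate.

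**The plan's principle already implies failure.** Carrying the pre-medication value forward, as at 24 hours, would bring baseline pain and the baseline MBS to 2 hours, and the patient would fail both. That is a sensible analogy, but the text does not make it. Success, exclusion and failure all remain arguable, which is a reason to state the rule.

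**The effect is small.** This stands. The behaviour is prohibited, patients rehearse the diary, the investigator reviews it in detail, and the only early-intake figure is zero. Against that, Section 1 says there are no data on patients using the device by themselves at home early in an attack, so zero cannot be assumed.

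**Non-responder scoring is not the only defensible rule.** This stands too: scoring the recorded state regardless of medication is compatible with Section 8.2.2. The case for the non-responder rule is its consistency with the plan's definition of sustained pain freedom.

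**Stronger readings that the documents do not support.**
- A reader might infer double-digit inflation, for example 0.30 × 0.50 = 15 points if 30% medicated and half of them were pain-free. No section supports such an intake. That product is also the gap between two scoring rules, and includes patients who would have responded to the device anyway.
- A reader might infer that early intake goes unrecorded. The diary covers the full 24 hours; what is missing is a rule for using it in the 2-hour outcomes.

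**Conclusion.** The gap is real, and it affects both primary outcomes and secondary outcomes 1 and 2. On a literal reading, a patient who medicates before the 2-hour rating and is then pain-free or MBS-free is a device success.

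The size is likely small: nil if nobody medicates early, and 1.1 to 3.7 points of pain freedom over assumed intakes of 5% to 11.6% with a 32.2% drug response. The lower figure at each intake (1.1, 2.5) assumes early medicators would respond to the device at 32.2%; the higher (1.6, 3.7) assumes none would.

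Neither scoring rule is shown to have the larger error. With d = 0.322 the non-responder rule errs more (1.6 and 3.7 down, against 1.1 and 2.5 up). With d = 0 the order reverses (0 down, against 1.6 and 3.7 up). The documents do not say which case is closer.

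A reader might also take the two rates as bounds on the device-alone rate. The non-responder rate is a conservative estimate. The as-observed rate is an upper bound only if medication never worsens the outcome and early medicators did not also shorten the session, and the plan keeps patients who stop early.

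This is a cheap improvement, minor in size.

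**What to change.** Add one sentence to Sections 3.1 and 8.2.3: patients who took any acute medication between the start of the session and the 2-hour rating are counted as non-responders for both primary outcomes and for secondary outcomes 1 and 2.

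Report the number of such patients and show the as-observed rates as a sensitivity analysis. If there are none, the two sets of rates are identical.

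Confirm with the sponsor that the diary records the time of intake. Sections 4.2.3, 6.5 and 7.1 do not explicitly ask for it, the diary form is not among the documents, and secondary outcome 3 needs it as well.

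The cost is one sentence in each of the two sections and one extra line in the results table. The downside is that a true device responder who medicates early is counted as a failure. No change to the rescue rule is proposed.
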